11.3 Sample handling and analysis

11.3.1 Collection

The only biospecimen involved in this study is blood. Blood draws of 5-10 mls would be performed as stated in the study activities table and before the dose of study drug. Blood specimen will be taken by a dedicated nurse or doctor.

The blood tests for **screening visit** will be sent to the **respective site's own laboratory.** The tests are:

- Free T₃, Free T₄, TSH
- HepBsAg, Anti HCV ab, HIV1/2 ab
- Full Blood Count
- Renal function test

- Liver function test
- Fasting blood sugar/ Random blood sugar (FBS/RBS)
- Fasting lipid profile

Subsequent FBS/RBS, renal profile for study treatment visits and follow up visits will also be sent to the respective site laboratory. Screening thyroid function tests results will not be analysed and therefore would not require specimens to be sent to a central laboratory.

Free T_4 , Free T_3 , TSH and TRAb levels for baseline and randomisation visit, study treatment visits (Visit 3 Week 2 and Visit 4 Week 4) and follow up visit (Visit 5 Week 6) will be sent to the centralised laboratory (Gribbles Pathology Laboratory Central Headquarters) for processing.

Request form with the patient's particulars shall be duly filled at the hospital site. Specimen should be individually packed in a specimen carrier bag with the request form. A call should be made by Site coordinator to Gribbles Pathology Careline number ([name]) for specimen pick up. Gribbles courier will be dispatched for specimen collection. Specimen transport will be done using a cooler bag (cool transport). Specimens will be collected by courier from the hospital site.

After checking the specimen from the courier, the laboratory staff will proceed to process the sample. Specimens are centifuged prior to sending it for analysis. Once centrifugation is done, the blood specimen is sent to the central headquarters laboratory for analysis. After test has been done, results are reviewed and if needed, validated before release.

Pre and post counselling test would be offered for HIV test in line with general practice and if positive be notified as per Malaysian law. Specimens would not be stored for future research.

11.3.2 Labeling

• The specimens will be labeled the study protocol number, subject number, subject initials, study day and name of test.

11.4 Laboratory analysis

#	Test	Method
1	Free T ₄	1. Type of kit : SIEMENS HEALTHCARE
		DIAGNOSTIC (SIEMENS HEALTHINEERS)
		2. Name of analyser : CENTAUR Xp
		Type of sample: Serum (recommended)
		4. Methodology: Direct Chemiluminescence
		competitive immunoassay
		5. Measuring range : 1.3 - 155 pmol/L
		6. Imprecision (CVs) : This assay exhibits total
		imprecision of \leq 7.3% CV
		7. Reference ranges :
		Adult : 9-25 pmol/L
2	Free T ₃	1. Type of kit : SIEMENS HEALTHCARE
		DIAGNOSTIC (SIEMENS HEALTHINEERS)
		2. Name of analyser : CENTAUR Xp
		3. Type of sample : Serum (recommended)
		4. Methodology : Direct Chemiluminescence
		competitive immunoassay
		5. Measuring range : FT3 : 0.3 - 30.8 pmol/L
		6. Imprecision (CVs) :
		This assay exhibits total imprecision of $\leq 3.7\%$
		7. Reference ranges :
		Adult : 3-6.5 pmol/L

		1. Type of kit : Siemens Healthcare Diagnostic
3	тѕн	(Siemens Healthineers)
		2. Name of analyser : Centaur Xp
		3. Type of sample : Serum (recommended)
		4. Methodology : TSH: 3 RD Generation Antibody
		capture.
		5. Measuring range : 0.008 - 150 μIU/L
		6. Imprecision (CVs) :
		This assay exhibits total imprecision of $\leq 3.8\%$
		7. Reference ranges :
		Adult : 0.4-4.7 mU/L
		1. Type of kit : Euroimmun Anti TSH Receptor
4	TRAb levels	(TRAb) ELISA (IgG)
		2. Name of analyser : EUROANALYSER
		3. Type of sample : Serum only
		4. Methodology : ELISA
		5. Measuring range: 0.16 to 40 IU/ml
		6. Imprecision (CVs): Interassay variation
		(n=20) with mean of 18.57 IU/ml is CV of
		7.6%
		7. Reference ranges :
		Negative: <1.0 IU/ml
		Positive: >1.0 IU/ml
		8. Storing and packaging of sampling instructions
		and methods: Serum sample storage 2-8°C for
		up to 14 days

12 DATA MANAGEMENT

Data will be written and collected from the CRF. Data collected will be transferred to an Excel sheet. Accurate and reliable data collection will be assured by verification and cross-check of 100% of the CRFs against the investigator's records (source document verification). The investigators will have access to the data and will be stored until the study period ends. The clinical data (hardcopy) will be archived and stored for 7 years. It will be destroyed after 7 years. The softcopy of the medical records of the subjects will remain in Electronic Medical Records (EMR) which will depend on the hospital's record office Protocol of Storage. The responsibility of the data handling and storage lies with the investigators and the sponsor.

13 STATISTICAL METHODS

13.1 Sample size and power considerations

The sample sizes estimations and analyses plan were made with the caveat that the three-treatment groups comparison is as little difference from carrying out a series of three independent trials, and to use conventional significance tests without adjustment as argued by Saville (1990)²⁰. Sample size and power considerations

Sample sizes were estimated by using PASS 11 software²¹. The estimations were based on primary objectives only.

Primary objective: To achieve 80% power to detect a 30% difference in the proportions achieving normal FT_4 between Group 3 (Carbimazole+Propanolol) and each of Group 1 (Cholestyramine + Carbimazole+ Propanolol) and Group 2 (Prednisolone+ Carbimazole+ Propanolol), 41 patients are needed in each group. The proportion achieving normal FT_4 in Group 3 was estimated to be 40%. (1) Allowing for 10% drop out rate, the sample size required is therefore 45 per arm. The test statistic used is the two-sided Z test with pooled variance.

The significance level was targeted at 0.05.

Primary objective: To achieve 80% power to detect a 30% difference in the proportions achieving normal FT_3 between Group 3 (Carbimazole+Propanolol) and each of Group 1 (Cholestyramine + Carbimazole+ Propanolol) and Group 2 (Prednisolone+ Carbimazole+ Propanolol), 41 patients are needed in each group. The proportion achieving euthyroid status in Group 3 was estimated to be 40%. (1) Allowing for 10% drop out rate, the sample size required is therefore 45 per arm. The test statistic used is the two-sided Z test with pooled variance. The significance level was targeted at 0.05.

Thus, the final sample size will be 45 per group.

13.2 Analysis

Data entry, cleaning and analyses will be done using SPSS version 21. Categorical data will be described by using proportions and numerical data will be described by using mean, median, standard deviation, and/or interquartile range, as appropriate. The analyses will be based on the intention-to-treat

13.2.1 Baseline Comparability

Baseline characteristics will be compared between the 3 groups using the appropriate descriptive statistics. No formal hypothesis test will be made for baseline comparison.

13.2.2 Efficacy Analysis

1. For the primary objectives, all comparisons of means between treatment will be analysed using one-way ANOVA and all pairwise comparisons of proportions will be analysed by using two-sided Z test and 95% confidence interval of the estimated difference will be calculated. Alpha level will be set at 0.05 and no adjustment will be made for the multiple pairwise comparisons. Analysis will be based on intention to treat and per protocol analysis.

2. For secondary objectives, all comparisons of means between treatment will be analysed using one-way ANOVA and all comparison of proportions will be analysed using chi-square test of independence.

Alpha level will be set at 0.05. Analyses will be based on safety set analysis.

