and hence decrease stimulation of the thyroid gland in Graves' disease¹⁴. Few case reports have documented its efficacy in situation where rapid control of hyperthyroidism is required. Ozawa in his case series documented that following oral administration of 30 mg daily dose of prednisolone with or without ATDs, both serum T_4 and T_3 concentrations decreased rapidly and reached euthyroidism within 2 weeks and subtotal thyroidectomies were performed uneventfully in all 4 cases¹⁷. Another study reported the addition of betamethasone 0.5mg 6 hourly, iopanoic acid 500 mg 6 hourly and propanolol 40 mg 8 hourly to 14 patients with hyperthyroidism submitted to subtotal thyroidectomy because ATDs have failed to control thyrotoxicosis and found that patients had normal T_3 levels by day 5 and T_4 reduction noted but has not reached normal levels by 5 days of treatment¹⁵. One study reported rapid normalization of thyroid function with prednisolone 20 mg daily as an adjunct when patients develop resistance to maximum treatment of carbimazole¹⁴. There were no reported serious side effects in the case series mentioned above.

Evidence in literature shows that adjunctive therapy such as cholestyramine and prednisolone may have a role to play in the management of hyperthyroidism. So far, studies on cholestyramine have proven its efficacy but they are small in size and have not been recommended in clinical guidelines. There are no clinical trials conducted in the asian population. A Cochrane systematic and current review is currently ongoing by Salazar et al. to asesss the efficacy of bile acid sequestrants as a standard adjunctive treatment therapy in hyperthyroidism and whether to recommend it in clinical practice guidelines¹⁸. This study would add weight to the ongoing systematic review. On the other hand, no clinical trials have been conducted to assess prednisolone as an adjunctive therapy to date and the safety profile unknown. We aim to compare the efficacy and safety profile of cholestyramine or prednisolone as adjunctive therapy to no adjunct. We also aim to compare the efficacy of cholestyramine and prednisolone as adjunctive therapy. We hypothesize that with the addition of cholestyramine or prednisolone to ATDs, we are able to achieve euthyroidism more effectively and rapidly compared to ATDs alone which may be useful in many crucial clinical situations described above.

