9.8 Assessment of efficacy

• Primary efficacy endpoints are:

1. Proportion of subjects with normal thyroid hormone levels: defined as serum free T_4 or serum Free T_3 levels measured at 2 and 4 weeks after initiation of study treatment.

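### Section 13.2.2 puts an undefined, unsized ANOVA of means under the primary objectives; label it supportive and replace it with baseline-adjusted log-scale pairwise ratios with intervals

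*Combined protocol and SAP*

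**What the plan says.** Section 13.2.2, item 1, covers the primary objectives with two methods. The first is for means: "For the primary objectives, all comparisons of means between treatment will be analysed using one-way ANOVA". The second is a pairwise two-sided Z test for proportions, with a 95% confidence interval for the difference. Alpha is 0.05, and no adjustment is made for multiple pairwise comparisons. The synopsis repeats both methods.

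The endpoint in 9.8 is a proportion only: "Proportion of subjects with normal thyroid hormone levels", using free T4 or free T3 at weeks 2 and 4. Section 13.1 is also about proportions only: "To achieve 80% power to detect a 30% difference in the proportions achieving normal" FT4, and the same again for FT3, with 40% assumed in Group 3.

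Section 6 compares each adjunct with no adjunct, and adds: "We also aim to compare the efficacy of cholestyramine and prednisolone as adjunctive therapy".

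Section 11.4 lists for the central laboratory "Measuring range : FT3 : 0.3 - 30.8 pmol/L", with an FT3 reference range of 3 to 6.5. FT4 is measured from 1.3 to 155 pmol/L, with a reference range of 9 to 25. Baseline FT4 and FT3 go to the central laboratory (11.1.2). Section 13.2 allows medians and interquartile ranges, but only for description.

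**The concern.** A test listed under the primary objectives should have a defined variable, time point and scale. The comparison of means has none of these and was not sized. As written, the analyst can choose after seeing open-label data between FT4 and FT3, week 2 and week 4, level and change, and raw and log scale.

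The method also fits the question poorly. The aims are three pairwise comparisons, but a one-way ANOVA gives one F test. Section 13.2.2 attaches pairwise comparisons and an interval to the proportions only. The means are the trial's only direct measure of how far hormone levels fall, so a reader would want a size of effect with its uncertainty.

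Hormone values in this population are also likely to have a long right tail, and a high FT3 may fall outside the stated measuring range. No rule for such a result is written.

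**Working it through.** **1. The plan's own figure.** Section 13.1 gives 41 evaluable and 45 randomised per arm, for 40% v 70% at 80% power. It states "The test statistic used is the two-sided Z test with pooled variance" and "The significance level was targeted at 0.05". With mean proportion 0.55:

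n = [1.96 × √(2 × 0.55 × 0.45) + 0.842 × √(0.4 × 0.6 + 0.7 × 0.3)]² / 0.30² = (1.379 + 0.565)² / 0.09 ≈ 42.

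Power is 79.0% at 41 and 82.8% at 45, so the proportion sizing reproduces closely. No size or power is stated for the means, so there is nothing to reproduce there.

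**2. Why skewness is expected.** On the central-laboratory range, entry FT4 exceeds 1.5 × 25 = 37.5 pmol/L, with no upper limit. The FT3 measuring limit is 30.8 / 6.5 = 4.7 times the upper reference limit. The FT4 limit is 155 / 25 = 6.2 times its upper reference limit.

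**3. Cost of not transforming.** The documents give no SD, so these are assumptions: log-normal values, log-SD s from 0.5 to 0.8, 45 per arm, adjunct median 0.7 times standard, pairwise t test at two-sided 0.05. On the log scale, power ≈ Φ(ln(1/0.7)/s × √(45/2) − 1.96). At s = 0.6 this is Φ(0.357/0.6 × 4.743 − 1.96) = Φ(0.86) ≈ 0.80.

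For FT3 the standard-arm median is set so that 40% are at or below 6.5: median = 6.5 × exp(0.253 s). Simulation (20,000 trials per row, FT3 above 30.8 set at 30.8) gives:

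| s | Median | Standard arm above 30.8 | Power, untransformed | Power, log | Gap (points) |
|---|---|---|---|---|---|
| 0.5 | 7.38 | 0.2% | 0.886 | 0.917 | 3 |
| 0.6 | 7.57 | 1.0% | 0.743 | 0.802 | 6 |
| 0.7 | 7.76 | 2.4% | 0.597 | 0.670 | 7 |
| 0.8 | 7.96 | 4.5% | 0.482 | 0.548 | 7 |

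For FT4, where the limit does not bind, untransformed v log power is 0.730 v 0.791 at s = 0.6 (6 points) and 0.451 v 0.556 at s = 0.8 (10.5 points; 11 in a repeat run).

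**4. Over-range rule, same FT3 scenarios.**

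| s | True mean difference | Set at 30.8 | Deleted |
|---|---|---|---|
| 0.5 | 2.51 | 2.50 (−0.4%) | 2.46 (−2%) |
| 0.6 | 2.73 | 2.67 (−2%) | 2.49 (−9%) |
| 0.7 | 2.97 | 2.77 (−7%) | 2.41 (−19%) |
| 0.8 | 3.28 | 2.84 (−14%) | 2.25 (−31%) |

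Setting values at the limit does not reduce the power of the untransformed test.

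**5. Baseline adjustment.** For correlation ρ between baseline and outcome, residual variance falls by the factor 1 − ρ²: 0.91, 0.75 and 0.51 for ρ = 0.3, 0.5 and 0.7. For an illustrative 0.5 SD pairwise difference with 41 per arm, power rises from 62% to 66%, 74% and 89%. In a separate simulation of the three-group test (41 per arm, 60% normal in both adjunct arms, s from 0.4 to 0.8), power was 56–64% untransformed with values at the limit and 61–68% on the log scale. With baseline added it was 67–73% (ρ = 0.3) and 82–84% (ρ = 0.6).

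**The case against.** **The primary result is safe.** This stands. An FT3 above 30.8 is not normal whatever number is entered, and the proportion analysis has its own pairwise tests and intervals.

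**A global F test for a supporting mean is conventional, and contrasts can follow it.** This is fair, but the plan neither calls the means supporting nor names contrasts. The absence of multiplicity adjustment is openly declared, so the case here rests on the undefined and unsized analysis and not on the error rate.

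**The plan does not say raw values.** Correct. No transformation is named, so untransformed analysis is the natural reading, but it is an inference.

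**A reader might infer that FT3 cannot be read above 30.8, that such results would be lost, and that the treatment difference would therefore collapse.** The documents do not support this. Section 11.4 gives a measuring range and is silent on dilution and on how over-range results are reported. Nothing says they are excluded, and the analysis is by intention to treat. The alarming figures need deletion plus a severe scenario: standard-arm median 18 pmol/L and s = 0.7, with 22% v 10% of values above the limit. There the difference falls from 6.9 to 2.7 pmol/L, and power is 0.38 for deleted untransformed values against 0.64 for log values at the limit. That contrast changes two things at once. With values set at the limit, untransformed power is already about 0.63, so the log scale adds only about 1 point. The scenario also implies 7% v 17% normal, far from the planned 40% v 70%. Section 13.1 ties the 40% to no visit, so week 2 could be worse than planned, but these figures remain an assumed-deletion worst case.

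**Conclusion.** The point holds as a low-severity improvement. An analysis that is neither defined nor sized sits among the primary ones, and its F test does not answer the pairwise questions.

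Leaving values untransformed costs roughly 4 to 8 points of pairwise power over most of the assumed range. It is about 3 at s = 0.5, up to about 11 for FT4 at s = 0.8, and about 1 in the severe FT3 scenario. Omitting baseline may cost more, depending on ρ. The assay limit is not the source of the power loss. At the plan's 40% control rate it affects about 0.2 to 4.5% of standard-arm FT3 values.

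Every power and shrinkage figure for the means rests on assumed log-normality, SDs and effect. With a 30% lower median, the 40% anchor implies about 68% normal in the adjunct arm at s = 0.5, close to the planned 70%, but only 58% at s = 0.8. A claim that the primary endpoint is biased, or that the assay limit by itself hides the effect, is not supported.

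**What to change.** Amend 13.2.2, item 1, and the matching synopsis line:

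- State that the proportion in 9.8 is the only primary analysis and that comparisons of means are supportive.
- Analyse log FT4 and log FT3 at weeks 2 and 4, each adjusted for its central-laboratory baseline value. Report the three pairwise ratios of geometric means with 95% confidence intervals.
- Keep any FT3 result outside 0.3 to 30.8 pmol/L in the analysis, set at the limit or handled by a censored-data model. Do not treat it as missing. Give counts per arm and add a rank-based check. Apply the same rule at baseline, where more values may be over range: 1% to 48% for an assumed median of 12 to 30 and log-SD of 0.4 to 0.6.

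The cost is SAP wording and a few lines of code, with no new data. There are two downsides. Effects are read as ratios instead of differences in pmol/L. Setting values at the limit still attenuates the difference, by about 0 to 14% on the pmol/L scale at the 40% control rate and by more if levels are higher (6.9 to 4.3 pmol/L in the severe scenario). A censored-data model avoids most of that attenuation if its distributional assumption is reasonable.

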Three treatment modalities are currently available for the management of hyperthyroidism: antithyroid drugs (ATDs), surgery, and radioactive iodine (RAI) therapy. Treatment for hyperthyroidism is aimed at restoring euthyroidism with ATDs while awaiting disease remission and resolution of autoimmunity or inducing permanent hypothyroidism with subsequent thyroxine replacement by total thyroidectomy or RAI therapy. Beta-blockers (for example propanolol and atenolol) are added to block beta-adrenergic tone for symptomatic relief of palpitations, tachycardia, tremulousness, anxiety, heat intolerance, fatigability and shortness of breath. There is currently no consensus on the "best" treatment option with various practices in different centers and countries. The choice of treatment depends on the cause of hyperthyroidism, patient's age and preference, severity of disease, glandular size, activity and severity of Graves' opthalmopathy, local practices and resources.

ATDs including methimazole, carbimazole, and propylthiouracil are effective treatments that inhibit thyroid hormone synthesis, and have clinically important immunosuppresive effects including reducing serum antithyrotropin receptor antibody concentration with time. Antithyroid drugs are an effective treatment option but these drugs take in most cases between 6 to 8 weeks to achieve euthyroidism. It has also shown to have the highest relapse rate at 52.7% compared to RAI (15%) and surgery (10%) in a recent meta analysis⁸. In addition 13% of patients on ATDs experienced adverse events with rash most common with methimazole and hepatic involvement with propylthiouracil⁸.

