Thyroid hormone is metabolized in the liver where it is conjugated to glucuronides and sulfates and excreted in the bile. Usually only 20% of circulating T₄ is excreted in the bile and released into the intestine and reabsorbed completing the enterohepatic circulation. However in the thyrotoxic states there is an increased enterohepatic circulation of thyroid hormones with an increased urinary and fecal excretion of both conjugated and FT_4^{9} . Cholestyramine is an anion exchange resin that binds T₄ in the intestine resulting in fecal excretion of T₄ thus reducing the enterohepatic circulation and absorption in hyperthyroidism. Cholestyramine has been used in cases of thyroid storm¹⁰. Cholestyramine has been studied as an adjunctive therapy to thionamides and found to be effective in reducing thyroid hormones rapidly. Solomon et al first studied the effects of cholestyramine powder (4g QID) on 15 thyrotoxic patients and shown a more rapid decline in all thyroid hormone levels in the cholestyramine group in the first 2 weeks (P<0.01)¹¹. Mercado et al similarly reported rapid decline in total and free T_4 and T_3 when cholestyramine 4g tds was added to methimazole and propanolol¹². Kaykhaei et al. demonstrated a similar efficacy with a lower dose of cholestyramine (2g BD vs 1g BD) with all patients in the cholestyramine group achieving euthyroidism in 4 weeks⁹. The main adverse effects are flatulence and constipation in 10% of cases and vomiting, diarrhea, indigestion, abdominal pain, abnormal stools, bloating, headache, and raised triglyceride levels in 1-10%, whereas muscle pain, raised liver enzymes and difficulty in swallowing are rare¹³. Patients in the trials above tolerated the drug well with only 2 reported hyperdefecation and complained of bad taste¹¹.

Steroids have been shown to be effective in controlling hyperthyroidism. It demonstrates immediate effects by inhibiting the conversion of thyroxine to triiodothyronine peripherally and also blocks the release of thyroxine from the thyroid gland. It may also have the potential to suppress the immune response

20

Confidential Date: 5th June 2017

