8.4.1 Inclusion criteria

- 1. Provision of written consent by subject or guardian.
- 2. Subject of either sex, more than 18 years of age
- 3. Subjects with moderate to severe overt hyperthyroidism (caused by Graves' disease).
 - Moderate to severe overt hyperthyroidism is defined as Free T₄>
 1.5 times upper limit of normal reference range and TSH below lower limit of reference range, who are either newly diagnosed or previously diagnosed and receiving ATDs currently.
 - •Graves disease is defined as hyperthyroidism coupled with clinical signs of symmetrical diffuse goiter, thyroid orbitopathy, or diffuse and vascular thyroid on ultrasound or positive TRAb antibody.
- 4. Female patients will either be
 - post-menopausal for > 2 years
 - Women of childbearing potential can be included if surgically sterile or using double contraception with at least one method being barrier contraception. Women of childbearing potential must have a negative pregnancy test at screening and at randomisation. Pregnancy tests will be repeated during each visit.

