11.1.2 Baseline visit (Week 0, Visit 2)

- Subjects who are eligible for the study after reviewing both inclusion and exclusion criteria will be called up for a baseline visit no longer than 1 weeks from screening visit.
- 2. Perform baseline measurements of vital signs (BP, HR, Temperature) and anthropometric measurements (Height (cm), Weight (kg) and BMI
- 3. Perform complete medical history and physical examination if not done during screening visit
- 4. Record any concomitant medications
- 5. The following baseline tests will be performed (Total of 6 mls of blood will be sampled). Thyroid function test and TRAb levels will be sent to central lab (Gribbles laboratory) whereas the other tests will be conducted at respective site.
 - a. Free T₄, Free T₃, TSH
 - b. TRAb levels
 - c. UPT (For all women of childbearing age)
 - d. ECG
 - e. ECHO if evidence of thyrotoxic cardiomyopathy
- 6. Complete relevant section/page of the CRF.
- 7. Subject who has fulfilled all inclusion and exclusion criteria and has completed baseline assessment will proceed to randomisation into any of the 3 treatment groups on the **same day**.
- 8. Refer to the study activities table below

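### Cheap improvement, not an error: the efficacy analysis leaves the central-laboratory baseline FT4 and FT3 unused; a baseline-adjusted risk difference, with the planned Z test as fallback, would use them

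*Combined protocol and SAP*

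**What the plan says.** All of the following is in the combined protocol and SAP.

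- **Analysis.** Section 13.2.2: "means between treatment will be analysed using one-way ANOVA and all pairwise comparisons of proportions will be analysed by using two-sided Z test", with a 95% confidence interval for each difference. No covariate, regression or change-from-baseline analysis is named.
- **Sample size.** Section 13.1 treats normal FT4 and normal FT3 as separate proportions and uses the same test: "The test statistic used is the two-sided Z test with pooled variance".
- **Use of baseline.** Section 13.2.1: "Baseline characteristics will be compared between the 3 groups using the appropriate descriptive statistics". No other use is stated.
- **Where baseline is measured.** Section 11.1.2: "Thyroid function test and TRAb levels will be sent to central lab (Gribbles laboratory"). Randomisation follows on the same day. Section 11.3.1 sends thyroid tests to that laboratory for the "baseline and randomisation visit, study treatment visits (Visit 3 Week 2 and Visit 4 Week 4"). Only the screening thyroid tests, run at each site, are left out of the analysis.
- **Who enters.** Section 8.4.1 requires FT4 above 1.5 times the upper limit of normal, sets no upper bound, and admits patients "who are either newly diagnosed or previously diagnosed and receiving ATDs currently".

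**The concern.** The outcome is whether a hormone has fallen into its reference range. For every patient the trial will already hold the pre-randomisation value of that hormone, from the same laboratory and assay. A patient who enters just above the FT4 threshold has less far to fall than one who enters far above it, and the mix of new and already treated patients widens the spread. Baseline is therefore plausibly prognostic, and an analysis that ignores it gives up precision that costs no patient, visit or blood sample. Withdrawn subjects are not replaced (section 8.4.5), so precision cannot be bought back later. The choice has to be fixed before outcome data are seen, because afterwards it could follow the result.

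**Working it through.** **1. The plan's own figure.** Inputs from section 13.1: 40% v 70%, two-sided alpha 0.05, 80% power, pooled variance.

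n = [1.960 × √(2 × 0.55 × 0.45) + 0.842 × √(0.40 × 0.60 + 0.70 × 0.30)]² / 0.30² = 41.97 per arm.

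Exact binomial enumeration of the pooled Z test gives 79.6% power at 40 per arm and 81.3% at 41. The stated 41 therefore reproduces, and the planned test is adequately powered on its own inputs.

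**2. Adjusted estimator.** Fit a logistic model with treatment and log baseline. For each patient, let m_a and m_0 be the predicted probabilities under adjunct arm a and under standard treatment, y the outcome (0 or 1), N the number of patients in the model, and n_a, n_0 the two arm sizes. Then

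D = m_a − m_0 + (N/n_a)(y − m_a) if the patient is in arm a, − (N/n_0)(y − m_0) if in the standard arm.

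The risk difference is the mean of D, and SE = √[Σ(D − mean D)² / (N(N − k))], where k is the number of model coefficients (4 with three arms, 3 with two). The target is still the risk difference that section 13.1 powers.

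**3. Simulation at 40% v 70%, 41 per arm.** Assumed: a latent normal outcome with correlation r to log baseline among enrolled patients; both adjunct arms at 70%; 20,000 trials per setting (Monte Carlo SE about 0.3 points). The documents give no r, so a range is shown.

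| r (assumed) | Z test power | Adjusted power | Change (points) | Variance ratio | Unadjusted n giving the same precision as 41 adjusted |
|---|---|---|---|---|---|
| 0 | 81.5% | 80.8% | −0.7 | 1.01 | 41/1.01 = 40.6 |
| 0.3 | 81.3% | 82.4% | +1.0 | 0.95 | 41/0.95 = 43.2 |
| 0.5 | 81.0% | 86.1% | +5.0 | 0.86 | 41/0.86 = 47.7 |
| 0.6 | 81.3% | 88.7% | +7.4 | 0.79 | 41/0.79 = 51.9 |

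Changes were taken before rounding. Independent repeats agree within Monte Carlo error.

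**4. 45 per arm, no dropout.** The planned pooled Z test has about 82% power; adjusted power is 83.3, 85.7, 89.3 and 91.8%. About 1.3 points of each rise come from using an unpooled variance (unpooled Z 83.4%), so the part due to baseline is about 0, +2, +6 and +8 points. Section 13.1 expects 10% dropout, so 41 per arm is the fairer case.

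**5. Type I error and coverage.** At 40% v 40% and 41 per arm, both tests run at about 5 to 6% (exact size of the pooled Z test 5.5%). At 45 per arm the adjusted test runs about half a point above the pooled Z test, whose exact size there is 4.9%. CI coverage at 40% v 70% was 94.2 to 94.7% in the main runs and as low as 93.6% in a separate run at r = 0.6.

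**6. The fallback rule.** Section 6 reports an earlier trial "with all patients in the cholestyramine group achieving euthyroidism in 4 weeks", and says of antithyroid drugs that "these drugs take in most cases between 6 to 8 weeks to achieve euthyroidism". An arm with all or no successes is therefore conceivable. Take prednisolone 70% v standard 40%, r = 0.5, 41 per arm, with cholestyramine at 98% or 99%. A rule that drops adjustment whenever any arm is saturated removes it from this comparison in 43 to 67% of trials, and power is 84.3% or 82.6%. A rule applied per comparison gives 86.0% or 86.8%.

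**The case against.** The strongest reply is that the Z test is pre-specified, valid and the basis of the sample size, so this is only a preference. The first part stands: nothing in the plan is wrong here, and a reader who inferred that the planned test is biased or underpowered would be mistaken. The second part does not follow. The change is specific, leaves the target unchanged, and costs at most about one point of power.

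The second reply is that the benefit rests on an undocumented r. That stands. The entry threshold narrows the range of FT4 and may weaken the correlation. If r is instead taken in an unselected population and baseline is cut at its median (an assumption), adjusted v Z power at 41 per arm is 81.0 v 81.3% for r = 0.3, 82.0 v 81.0% for r = 0.5 and 84.4 v 81.5% for r = 0.6. The gain is then about 0, 1 and 3 points. The table above applies only if r refers to enrolled patients.

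Three stronger readings are tempting and are not supported:

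- That rates near 0% or 100% count against the plan. The test that loses power there is the Wald test of a logistic treatment coefficient, which nobody planned; the Z test has about 100% power at 40% v 95%. This only governs how the adjusted analysis should be built.
- That an interval about 40 points wide is too wide for a 30-point target. The half-width of about 20 points is what 80% power implies.
- That one-way ANOVA wastes baseline information on means. No mean endpoint is named in the synopsis or section 9.8, and section 13.2.2 does not say whether means are raw values or changes.

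**Conclusion.** The point holds as an optional but worthwhile improvement. The efficacy analysis does not use a prognostically plausible, same-laboratory baseline that the trial already collects. At 41 per arm and 40% v 70%, the effect of adjustment runs from about −1 point of power (r = 0) to about +7 points (r = 0.6), with the variance of the risk difference at 1.01 to 0.79 of its unadjusted value. With r of 0.3 or less the gain is small or nil. These figures rest on an assumed r among enrolled patients and on the simulation model described. Type I error is close to that of the planned test at 41 per arm and slightly higher at 45. The documents do not support calling the gain certain. Adjustment also leaves other matters open: whether the endpoint in section 9.8 means FT4 or FT3 or both, the two visits, the unadjusted pairwise tests, and missing outcomes.

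**What to change.** In section 13.2.2 pre-specify, for FT4 and FT3 separately (as in section 13.1) and for each visit:

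1. A logistic model with treatment (three levels) and the log central-laboratory baseline of the same hormone.
2. The standardised risk difference for each pairwise comparison, with both the p-value and the 95% CI taken from it, not from the treatment coefficient.
3. A fallback applied per comparison: use the planned Z test and its CI only if one of the two compared arms has all or no successes, or the model does not converge. If only the third arm is saturated, fit the model to the two compared arms.
4. Baseline values above the measuring range in section 11.4 set to its limit, and a missing baseline set to the pooled mean of the log values.
5. The unadjusted Z test reported in every case as a sensitivity analysis.

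If mean FT4 or FT3 is compared at all, name the variable and use ANCOVA on the same baseline; this is a conditional side point.

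Cost: a few lines of text and a little programming. If SPSS version 21 (section 13.2) has no ready routine, the formula for D needs only the fitted coefficients and column arithmetic on the data sheet described in section 12. If baseline proves not to be prognostic, the price is about 1 point of power.
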